## Statistical Analysis Plan

**Analyses** will be conducted with SAS v9.4 and Mplus. Descriptive statistics will be generated for outcome variables and potential covariates according to PAC/PWL. Non-normally distributed variables will be transformed and between-group baseline differences for outcomes and covariates will be assessed. All study hypotheses will be tested using Intent-To-Treat (ITT) methods, with multiple imputation incorporating auxiliary variables used to handle missing data, and all primary analyses will be performed using imputed data sets. We will also conduct additional, less conservative complete-case analyses and we will compare these results to the ITT analyses.

For **Aim 1**, the primary outcome is between-group (PAC vs. PWL) differences in adolescent  $\Delta\text{BMI}_{4-12m}$ . Both within- and between-group effects of treatment on  $\Delta\text{BMI}_{4-12m}$  will be compared via linear mixed model analyses. This model will also be used for **Secondary Aim** analyses, to examine within- and between-group changes in adolescent energy intake (kcal/d); energy expenditure (kcal/d); and PA (min/wk) from 4-12m. For **Aim 2**, both within- and between-group effects of treatment on parental variables, home food and exercise environment, and adolescent perceived autonomy support from 0-4m will be compared via linear mixed model analyses. Multivariate linear regressions will examine the impact of 0-4m changes in these variables on adolescent weight loss maintenance ( $\Delta\text{BMI}_{4-12m}$ ). We will then evaluate whether the treatment effects for weight loss maintenance are mediated by *authoritative parenting* using Structural Equation Modeling (SEM). Model fit will be compared using chi-square analyses. To evaluate whether BE/LOC moderates the effects of treatment on authoritative parenting and/or authoritative parenting on weight loss maintenance, we will apply a moderated mediation model by adapting the SEM model above using a multiplicative regression approach. In the **Exploratory Aim**, we will evaluate the effect of concordance of parent and adolescent variables on adolescent weight loss maintenance using linear mixed models. Concordance will be defined by the possible response pairs or using difference scores for categorical and continuous variables, respectively.

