**Power analyses** were conducted using SD and effect sizes from the pilot for between-group (PAC/PWL)  $\Delta\text{BMI}_{7m}$ , projected to 12m (the primary endpoint of this trial;  $\Delta\text{BMI}_{4-12m}$ ). We assumed a constant rate of weight change and increased SD. A proposed sample size of 210 (105 dyads per arm) will have >80% power (2-sided, alpha=.05) to detect significant *between-group* differences in adolescent  $\Delta\text{BMI}_{4-12m}$ , with SD≤2.9, which corresponds to a small to moderate effect size (Cohen's  $d=.39$ ). The 12m projections, with SD≤1.7, and N=210 provide 80% power to test BE/LOC as a moderator. This sample size also provides 80% power to evaluate authoritative parenting as a mediator in a partially mediated model. We used effect sizes to power this trial given lack of agreed-upon clinically significant thresholds for adolescent BMI change.

Protocol Changes		
DATE	CHANGE	REASON
June 2018	Modified adolescent baseline calorie goal ranges. Throughout the intervention, baseline female calorie range goals ranged from 1200-1400 to 1700-1900. Baseline male calorie range goals ranged from 1400-1600 to 2400-2600.	Enhanced specificity based on starting height and sex.
March 2020	
 
1. Intervention sessions transitioned from in-person to virtual (Zoom) due to COVID-19.
 
2. Exercise program transitioned from in-person to pre-recorded exercise workout videos provided on a private YouTube channel for participants accessible from study website. Heart rate monitors were no longer worn.
 
3. Transitioned to remote assessments due to restrictions. Calibrated scales and stadiometers were left on participants' porches with video instructions on obtaining height and weight measurements. Recalls were conducted over Zoom.
 
4. Cooking classes transitioned to virtual. Participants were provided a gift card and ingredient list to purchase supplies needed prior to classes led by chefs.
 
	COVID-19 restrictions and mandates
August 2020	Resumed in-person assessments but continued to offer remote assessments. Remote assessments transitioned to being conducted by assessor in the participant home (or designated location) as an option to accommodate families' comfort level.	Virginia now in Phase 3 of re-opening. In-person interactions permitted with proper protections in place.

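### The only inferential procedure named for the Aim 2 mediation question is a chi-square comparison of unnamed models; no estimate, interval or test of the indirect effect is specified

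*Combined protocol and SAP*

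**What the plan says.** In the Statistical Analysis Plan, the Aim 2 text first sets out mixed models for treatment effects on parental, home and autonomy-support variables over 0-4 months. It then sets out regressions of ΔBMI over 4-12 months on the 0-4 month changes in those variables. The mediation step follows: "We will then evaluate whether the treatment effects for weight loss maintenance are mediated by" authoritative parenting, using SEM. The next sentence is the only inferential statement attached to that model: "Model fit will be compared using chi-square analyses".

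The moderated-mediation analysis for BE/LOC is obtained "by adapting the SEM model above using a multiplicative regression approach", so it inherits whatever the SEM step leaves open. The power paragraph adds: "This sample size also provides 80% power to evaluate authoritative parenting as a mediator in a partially mediated model". No path sizes, test or alpha accompany that claim. Analyses "will be conducted with SAS v9.4 and Mplus".

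The plan does not identify the competing models, their degrees of freedom or a decision rule for mediation. It specifies no estimate, interval or test of the indirect effect.

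**The concern.** Mediation is a claim about the product a×b, where a is the effect of treatment on parenting and b is the effect of parenting on ΔBMI given treatment. A fit comparison answers that question only if the constraint being tested is a×b=0 or its equivalent. The two comparisons most often meant by such a sentence test something else. Full against partial mediation tests the direct path c'. Dropping both mediator paths tests a=b=0 and rejects when either path is non-zero.

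The second case matters here. PAC trains parents in an authoritative style, whereas PWL treats the parents' own weight and does not directly address supporting the adolescent (Parent Interventions, parts a and b). A non-zero a with an uncertain b is therefore a plausible outcome. A fit comparison could then favour the mediated model without evidence that parenting affects BMI. At stake is the trial's conclusion about mechanism, which has its own power claim. If the fit comparison is not the criterion, none is stated, and one could be chosen after the results are seen.

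**Working it through.** **Inputs from the power paragraph.** 210 dyads, 105 per arm; "2-sided, alpha=.05", stated for the primary comparison and assumed here for mediation; d=0.39.

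**Assumptions.** The documents give no path sizes, so every a, b and c' below is assumed. The value 0.39 is the plan's BMI effect size, used only as a convenient scale. The model is M = aX + e₁ and Y = c'X + bM + e₂, with X = ±0.5, unit residual SDs and complete data.

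**Step 1: the plan's own figures.** Primary power = Φ(0.39×√(105/2) − 1.960) = Φ(2.826 − 1.960) = Φ(0.866) = 80.7% (80.3% with the t distribution), so the stated figure of more than 80% reproduces. The 80% for the mediator cannot be checked, because it has no inputs.

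**Step 2: what each comparison tests.**
- Full against partial mediation: c'=0, 1 df. It says nothing about a or b.
- Mediator paths dropped: a=b=0, 2 df. It rejects if either path is non-zero.
- Constraint a×b=0: in this model the statistic is the smaller of the two 1-df statistics for a=0 and b=0, so it equals requiring both to be significant. This is a valid test.

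**Step 3: analytic check of the 2-df comparison.** With a=0.39 and b=0, the noncentrality is 210×0.25×0.39² = 7.99. Against the 5% critical value on 2 df, this gives a rejection rate of about 72%, although a×b=0.

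**Step 4: simulation, 20,000 trials per row.**

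| True a, b, c' | Full mediation retained | 2-df test rejects | a and b both significant | Full retained and total effect significant |
|---|---|---|---|---|
| 0.39, 0, 0 | 94.9% | 71.8% | 4.4% | 0.9% |
| 0.39, 0, 0.39 | 21.1% | 71.3% | 4.4% | 2.9% |
| 0, 0.39, 0.39 | 19.8% | 99.9% | 5.0% | 2.2% |
| 0.39, 0.26, 0.29 | 46.3% | 99.1% | 77.8% | 24.3% |
| 0.39, 0.39, 0.24 | 59.6% | 100% | 81.1% | 35.5% |

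The first three rows have no indirect effect; the last two do.

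**Step 5: interval for a×b (Monte Carlo, 4,000 trials per scenario).** With a=0.39 and b=0, the 95% interval excludes zero in 3-4% of trials. With a=0.5 and b=0.25, it excludes zero in about 88-90%. In that second setting, requiring a significant total effect plus retained full mediation succeeds in about 12% of trials when c'=0, because the total effect is only 0.5×0.25 = 0.125. It succeeds in about 32% when c' = 0.39 − 0.125 = 0.265, because full mediation is then untrue and is often rejected.

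**The case against.** A reader might infer that the plan declares mediation by chi-square. The text does not say so. The sentence is about model fit, and comparing fit is a routine SEM step that can sit beside path estimates. This objection stands: the defect is a missing criterion, with the one named procedure unsuited to the question in its usual forms. It is not a stated wrong rule.

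A reader might also infer that no chi-square test can address an indirect effect. That is too strong. A difference test of a×b=0, or separate tests of a=0 and b=0 that must both reject, held the false-positive rate at no more than 5.1% in every null scenario simulated. The plan names neither.

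Three further points have force.
- The plan asks about mediation of a treatment effect and refers to a partially mediated model, so an analyst might not claim mediation without a significant total effect. Requiring one as well as retained full mediation brings false positives down to 0.2-2.9%. The plan does not state this requirement, and it loses most of the power (working, steps 4 and 5).
- The earlier Aim 2 models approximate the a and b paths, so a null b would probably be noticed. They are not tied to a mediation rule.
- PWL is an active, contact-matched comparator, so a non-zero a is a hypothesis, not a fact. The rejection rates are therefore conditional.

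Finally, a bootstrap or Monte Carlo interval is not the only sound choice; joint significance of a and b performs about as well.

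**Conclusion.** The concern holds as a gap in specification with practical consequences. For mediation, the plan names only a fit comparison between unidentified models and gives no estimate, interval or test of a×b. Under the assumed path sizes, the usual comparisons either reject often when there is no indirect effect (about 70% at a=0.39, b=0, against 3-4% for the interval) or, with a total-effect requirement added, miss most real ones (about 12-32% power against 88-90% at a=0.5, b=0.25).

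These figures rest on complete data, N=210, unit residual SDs and path sizes that the documents do not supply. They show how the procedures behave and do not predict this trial's result. Nor do they show that the 80% mediator power is wrong, only that it cannot be checked. The point concerns Aim 2 and its moderated-mediation extension. It does not touch the Aim 1 comparison, whose power reproduces.

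**What to change.** Replace the fit-comparison sentence with a rule along these lines: mediation will be concluded if the 95% confidence interval for the indirect effect a×b in the partially mediated model excludes zero; chi-square fit comparisons are descriptive.

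The interval may be bootstrap or Monte Carlo, or the rule may use an equivalent test such as joint significance of a and b. Whichever is chosen, say how it is combined over the multiply imputed data sets. For BE/LOC, specify a matching interval for the moderated-mediation effect. In the power paragraph, give the a, b and c' values, the alpha and the test behind the 80%, and make that test the one used in the analysis.

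The cost is a few sentences of SAP text and one power calculation. Mplus is already planned, and no new data are needed. The change should be dated, and made before any mediation results are examined.

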**NCT03851796**

**OCTOBER 13, 2025**

## STUDY PROTOCOL

We propose to conduct a 2x5 repeated-measures, randomized clinical trial to test study aims and hypotheses. We will randomly assign families to either: Parents as Coaches (PAC) or Parent Weight Loss (PWL). All adolescents will participate in the 4-month TEENS+ protocol. The proposed intervention is modeled after our pilot and designed to test its efficacy in a fully powered trial over 1-year follow-up. Assessments will be conducted at 0, 2, 4, 8 and 12 months (m). The primary dependent variable of interest is  $\Delta$ BMI at 12m ( $\Delta$ BMI4-12m), representing adolescent weight loss maintenance. Eight waves of adolescent/parent dyads will be stratified by sex and race and randomized to TEENS+PAC or TEENS+PWL. We will recruit 210 families (105 randomly assigned to each condition) using established strategies, and employ a block randomization scheme, stratified for adolescent sex and race, to ensure equal group allocation on these variables. Participants who consent/assent, meet eligibility criteria and complete baseline assessments will be eligible for randomization and assigned to either TEENS+PAC or TEENS+PWL. To reduce contamination, adolescents will be in groups according to their parents' assignment. Participants will be informed of their intervention assignment at the first group meeting.

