### **Assessments.**

Assessments of anthropometrics, dietary intake, PA, parenting and home environment variables will be completed by trained, masked assessors at 0, 2, 4, 8, and 12m, with the primary endpoint at 12m follow-up. Measures for parents and adolescents include the following: anthropometrics (after a 12 hour fast), dietary intake, physical activity, parenting style, eating disorders and depression, parent/child conflict, weight control strategies (physical activity, dietary behaviors, and self-monitoring), Parents will also complete measures assessing demographics, child feeding behaviors, the home food and home exercise environments, self-efficacy to support their child's healthy weight management, and readiness to change. Adolescents will also complete measures assessing perceived autonomy support from their parents, family social support for eating and exercise, and perceptions of parent's dieting behaviors. Parents and adolescents will complete exit surveys at the end of treatment (4 month). Attendance and adherence to program components will be monitored, and interventionists will maintain fidelity checklists after each session. Formal fidelity monitoring will also be conducted.

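### Does an undefined BE/LOC moderator, with two moderated paths joined by and/or, call for a change to the plan?

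*Combined protocol and SAP*

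**What the plan says.** BE/LOC occurs in two sentences, both in the Statistical Analysis Plan.

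- The Aim 2 text sets the question this way: "To evaluate whether BE/LOC moderates the effects of treatment on authoritative parenting and/or authoritative parenting on weight loss maintenance". It answers it with a moderated mediation model, built "by adapting the SEM model above using a multiplicative regression approach". The sentence just before says that the fit of the mediation models is compared by chi-square.
- The power paragraph states: "The 12m projections, with SD≤1.7, and N=210 provide 80% power to test BE/LOC as a moderator".

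Neither sentence expands the abbreviation or gives a respondent, instrument, visit, scoring or cut-off. The nearest candidate is in the Assessments section: "Measures for parents and adolescents include the following: anthropometrics (after a 12 hour fast), dietary intake, physical activity, parenting style, eating disorders and depression". That list covers both members of the dyad, at 0, 2, 4, 8 and 12 months, and is not linked to BE/LOC. The table of assessment measure changes does not mention BE/LOC.

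No multiplicity adjustment or hierarchy appears anywhere. The only stated alpha (.05, two-sided) belongs to the primary comparison.

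**The concern.** Four choices appear open: parent or adolescent score, which visit, continuous or cut score, and which path counts as the main test. Each combination is a different hypothesis on the same 210 families. With no true moderation, trying several and reporting any hit would push the false-positive rate above 5%. With true moderation, the scoring or the respondent could decide whether it is found. A score taken after randomisation could itself be changed by treatment and would not be a clean moderator.

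The gap stands out because the same section is more specific elsewhere. It sets 0-4 month and 4-12 month windows for other Aim 2 variables, and for the Exploratory Aim it separates variable types: "Concordance will be defined by the possible response pairs or using difference scores for categorical and continuous variables, respectively". The moderator also has its own power claim and is not labelled exploratory. At stake is the conclusion about for whom PAC or PWL works through parenting.

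**Working it through.** **1. The plan's primary power, as a check on method.** Inputs from the power paragraph: 105 per arm, d = .39, two-sided alpha .05.
- Noncentrality = .39 × √(105/2) = 2.826.
- Power = Φ(2.826 − 1.960) = 80.7% (80.3% with the noncentral t). The plan says above 80%, so this reproduces.

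**2. The moderator's 80%.** Inputs given: SD at most 1.7 and N = 210. The interaction size, the path and the moderator's distribution are not given, so the figure cannot be reproduced. An arm-by-binary-moderator contrast on BMI change illustrates how far it depends on them:
- SE = 1.7 × √2 × √(1/(105q) + 1/(105(1−q))), with assumed prevalence q.
- The interaction detectable with 80% power is (1.960 + 0.842) × SE: 1.31 BMI units at q = .5, 1.43 at .3, 1.64 at .2 and 2.19 at .1.

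This contrast is neither planned path. One path has parenting as its outcome; the other is parenting by BE/LOC on BMI change. It therefore does not test the plan's figure.

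**3. Error rate from what is written.** Two paths, each at .05:
- Independent tests: 1 − .95² = 9.75%. Under any dependence the bound is .05 + .05 = 10%.
- If both product terms are judged by one joint test in the one model, the rate is the nominal 5%.

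**4. Error rate from a search.**
- Two paths by two respondents, independent: 1 − .95⁴ = 18.5% (18.0% to 18.3% in simulation).
- Adding two scorings: 27% to 30% in simulation.
- The simulations fitted separate least-squares regressions rather than the planned SEM, with an assumed parent-adolescent correlation of 0 or .3 and cuts at 20% or 40%. They also need an analyst who runs every version and reports any hit.

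**5. Power by scoring.** Assume a normal score and an interaction with exactly 80% power when the score is kept continuous (noncentrality 2.815 on 206 degrees of freedom). A cut at prevalence p multiplies the noncentrality by φ(z)/√(p(1−p)):

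| Cut | Factor | Power |
|---|---|---|
| 50% | .798 | 61% |
| 30% | .759 | 57% |
| 20% | .700 | 50% |
| 10% | .585 | 37% |

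The SD cancels, so these figures do not come from the plan's 1.7. They show the general cost of dichotomising.

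**6. Cost of a formal adjustment.** Bonferroni over two paths gives .025 each. A test with 80% power at .05 falls to Φ(2.802 − 2.241) = 71.2%. Holding 80% would take 210 × ((2.241 + 0.842)/2.802)² = 254.3, so about 255 families.

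**7. How far the text narrows the open choices.**
- *Visit:* Aim 2 takes parental change over 0-4 months. For the treatment-to-parenting path, only the month 0 value comes before both treatment and that change. One moderator serving both paths in one model is then naturally the baseline value. For the second path alone, a later visit would also precede the 4-12 month outcome, so the text does not force this.
- *Scoring:* product terms accept a continuous or a binary score, and the instrument's usual scoring would apply.
- *Path:* a single adapted model estimates both.
- *Respondent:* this is the one choice the text does not narrow. The outcome is the adolescent's, the mediator is the parent's, and both are measured.

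**The case for a change.** The strongest case for acting is that a hypothesis with its own 80% power claim ought to be identifiable from the plan, and this one is not. The respondent matters in particular. If moderation runs through one family member and the other's score is tested, with an assumed correlation of .3, it is detected in only about 12% to 13% of simulated trials. A single SEM can hold both paths, but the plan names neither a joint test nor an index of moderated mediation. The reference cited for the method can settle the model type but not this trial's moderator. Writing the definition down would take a few sentences.

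Much of that stands as description. The definition is absent, the chi-square sentence does not clearly extend to the moderated model, and SD 1.7 sits beside 2.9 for the primary outcome without explanation. What does not stand is the inference that the choices will be made after seeing results. The document is short and does not set out its hypotheses in full, so silence here is not evidence of a search. Whether to adjust across two separately reported paths in a secondary mechanism analysis is a matter on which reasonable statisticians differ, and the adjustment has the price in step 6.

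**Conclusion.** No change to the plan follows. The omission is real, but no stated rule or figure is shown to be wrong. Analysts would fill it in the ordinary way, with a baseline score from a named respondent on its usual scale, and report both paths from the one model.

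The only error rate that follows from the written text is 9.75%, and only if the two paths are tested separately and independently; 10% is the ceiling. The higher rates and the loss of power from cutting a score rest on assumed prevalence, correlation, normality and analyst behaviour, none of which the documents give. The moderator's 80% power remains unverified either way.

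The moderation result should be read as secondary evidence on mechanism. Aim 1, its 210 families and its reproduced 80.7% power do not depend on it.

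### Exploratory Aim: a difference score for continuous parent-adolescent variables, with no parent or adolescent main effects stated, can pass off one member's own effect as concordance

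*Combined protocol and SAP*

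**What the plan says.** The Exploratory Aim has two sentences in the Statistical Analysis Plan. The first gives the purpose and model: "we will evaluate the effect of concordance of parent and adolescent variables on adolescent weight loss maintenance using linear mixed models". The second gives the definition: "Concordance will be defined by the possible response pairs or using difference scores for categorical and continuous variables, respectively".

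The plan does not say whether the difference is signed, absolute or squared. It does not say whether the parent's and adolescent's own scores enter the model, which variables are compared, or whether levels or changes are differenced. It gives no alpha or power for this aim.

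The Assessments section shows which variables could be compared: "Measures for parents and adolescents include the following: anthropometrics (after a 12 hour fast), dietary intake, physical activity, parenting style" and others. Many of these are continuous, so the difference-score rule would govern much of the aim.

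**The concern.** A plain difference score is one value minus the other, here P − A. That is a linear combination of the two members' own scores. A single slope on it forces the parent and adolescent effects to be equal and opposite, and tests that contrast. Agreement is a different matter: it concerns how close the two values are, whichever is larger.

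The outcome is the adolescent's own BMI change, so for diet or activity the adolescent's own behaviour may well matter more than the parent's. In that situation the score would be significant without any concordance effect. The trial could then report that parent-adolescent agreement helps or harms weight maintenance when the data show only that the adolescent's own behaviour does. A real effect of agreement could also go unseen.

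**Working it through.** **The plan's own figure.** The only power figure that bears on this sample is for Aim 1: "A proposed sample size of 210 (105 dyads per arm) will have >80% power" ("2-sided, alpha=.05"), at d = 0.39. With 105 per arm, the normal approximation gives 80.7% and the noncentral t gives 80.3%. The figure reproduces. The documents give none for the Exploratory Aim.

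**Inputs.** N = 210 is from the plan. Two-sided 0.05 is stated for Aim 1 and assumed here. Everything else is assumed: parent and adolescent SDs of 1, correlation ρ = 0.3 (range 0 to 0.6), residual SD 1, member effects of 0.2 or 0.3, a concordance effect of 0.3 per unit of |P − A|, and mean gaps m of 0, 0.5 or 1 SD. There is one outcome per adolescent, with arm as a covariate.

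**Signed score, no concordance effect.** Let Y = bP·P + bA·A + error and D = P − A. Then Cov(Y, D) = (bP − bA)(1 − ρ) and Var(D) = 2(1 − ρ), so the slope on D is (bP − bA)/2 at any ρ. At ρ = 0.3, Var(D) = 1.4.

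- bA = 0.3, bP = 0: slope size 0.15; residual variance 1.09 − 0.0225 × 1.4 = 1.0585; noncentrality 0.15 × √(210 × 1.4 / 1.0585) = 2.50; rejection Φ(2.50 − 1.96) = about 70%.
- bA = 0.2, bP = 0: slope size 0.10; residual variance 1.04 − 0.014 = 1.026; noncentrality 1.69; rejection about 39%.
- bA = 0.3, bP = 0.2: slope size 0.05; simulated rejection about 11% to 12%.
- bA = bP: slope 0; rejection about 5%.

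**Signed score, true effect of |D|.** For normal D with mean m and SD σ = √1.4 = 1.183, Cov(|D|, D) = σ²(2Φ(m/σ) − 1). The slope on D is therefore 0.3 × (2Φ(m/σ) − 1): 0 at m = 0, about 0.10 at m = 0.5, about 0.18 at m = 1. The signed score sees nothing at equal means and something when the means differ.

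**Absolute score entered alone.** By the same result, Cov(A, |D|) = −(1 − ρ)(2Φ(m/σ) − 1). This is zero at equal means but not otherwise: −0.7 × 0.602 = −0.42 at m = 1. The adolescent's own effect then leaks into |D|.

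**Simulation** (ρ = 0.3; 4,000 trials per scenario, Monte Carlo standard error at most 0.8 points). Entries are the percentage of trials in which the concordance term is significant.

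| Truth | Mean gap | Signed alone | Absolute alone | Absolute + both main effects |
|---|---|---|---|---|
| Adolescent effect 0.3 only | 0 | 69 | 6 | 5 |
| Adolescent effect 0.3 only | 0.5 SD | 69 | 23 | 5 |
| Adolescent effect 0.3 only | 1 SD | 69 | 49 | 5 |
| Equal effects 0.3 and 0.3 | 0 | 5 | 5 | 5 |
| \|P − A\| effect 0.3 | 0 | 6 | 85 | 84 |
| \|P − A\| effect 0.3 | 0.5 SD | 38 | 91 | 80 |
| \|P − A\| effect 0.3 | 1 SD | 84 | 97 | 64 |

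A mean gap only moves the intercept of the signed model, so its false-positive rate does not change with the gap. Across ρ = 0, 0.3, 0.6, the signed score's false-positive rate (adolescent effect 0.3 only) is 84%, 70%, 48%. The full model's power at equal means is 95%, 84%, 62%.

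**Main effects do not rescue a signed score.** With one member's score beside D, the slope on D becomes the other member's main effect. With both, D is perfectly collinear.

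**The case against.** The strongest reply is that the plan never says signed. An absolute difference fits the text equally well, and at equal means it behaves properly even alone (6% false positives, 85% power). On that view only a detail is missing. The point about the text stands, and a reader should not infer that the plan prescribes a signed score or that the aim cannot be answered. It does not clear the plan, because an absolute score alone still gives 23% to 49% false positives once the means differ. A gap is plausible for physical activity: the adolescent goal is at least 1 hour a day (420 minutes a week), while the PWL parent goal is at least 250 minutes a week. These are targets, not observed means.

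Three further objections also stand:

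- False positives with the signed score need unequal member effects. The 39% to 69% range assumes no parent effect at all.
- Nothing in the documents shows that differences average zero, so it does not follow that a signed score would always miss concordance. With a mean gap it picks up part of it, still mixed with main effects.
- The remedy is not perfect. A purely curved adolescent effect (0.2 × A²) makes the absolute or squared term significant in 24% to 26% of trials even with both linear main effects present. Standardizing within role removes a real raw gap: at a 1 SD gap, power for a raw |P − A| effect is about 45%, against 65% on the raw scale.

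**Conclusion.** The concern holds for continuous variables in the Exploratory Aim. On either natural reading, a difference score without both members' main effects can mislabel a main effect as concordance. Signed, it does so whenever the two members' effects differ: about 39% to 69% of trials if only the adolescent's value matters, 11% to 12% at effects of 0.3 and 0.2, and the nominal 5% when they are equal. Absolute, it does so when the means differ. The signed score also has almost no power for true concordance at equal means (about 6%). These sizes rest on assumed effects, correlation and mean gaps; the algebra for the signed slope needs only equal variances.

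A reader might extend this to the categorical variables. The documents do not support that: response pairs entered as a factor already carry both members' effects. Nor does it reach Aim 1, Aim 2 or the sample size. Being exploratory limits the consequence, but does not make the score measure agreement.

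**What to change.** For continuous variables, state in the Statistical Analysis Plan that:

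1. concordance is the absolute (or squared) parent-adolescent difference;
2. the parent and adolescent scores both enter as main effects;
3. the concordance test is the coefficient of the difference term only;
4. scores are on the raw scale or standardized within role, with the reason. Raw scores ask whether the two values are close; standardized scores ask whether the two members stand at similar places within their own groups;
5. a sensitivity model adds the squared parent and adolescent scores, so that curvature in one member's effect is not read as concordance.

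Leave the categorical rule as it is. The cost is a few lines of text and two model terms (two more in the sensitivity model), with no new data. Some power is lost when the means are far apart: at ρ = 0.3, from about 84% at equal means to about 64% at a 1 SD gap.

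### The stated >80% power reproduces only if all 105 adolescents randomized per arm supply a 4-12 month BMI change; no retention rate or allowance is stated (minor)

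*Combined protocol and SAP*

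**What the plan says.** The Study Protocol section sets the recruitment target: "We will recruit 210 families (105 randomly assigned to each condition) using established strategies". It describes the intervention as "designed to test its efficacy in a fully powered trial over 1-year follow-up".

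The power paragraph in the Statistical Analysis Plan uses the same number: "A proposed sample size of 210 (105 dyads per arm) will have >80% power (2-sided, alpha=.05) to detect significant" differences between arms in the primary outcome, with an SD of at most 2.9 and d = .39. Its stated inputs are the pilot SD and effect sizes projected to 12 months, a constant rate of weight change and an increased SD. The moderator power is also tied to N=210, and the mediator power to the same sample size.

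For Aim 1, "the primary outcome is between-group (PAC vs. PWL) differences in adolescent" BMI change from month 4 to month 12. The Assessments section says measures will be "completed by trained, masked assessors at 0, 2, 4, 8, and 12m, with the primary endpoint at 12m follow-up".

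The Statistical Analysis Plan also provides for missing data, "with multiple imputation incorporating auxiliary variables used to handle missing data", and says that "all primary analyses will be performed using imputed data sets". It adds: "We will also conduct additional, less conservative complete-case analyses". No section gives an expected retention or attrition rate, or an inflation of the sample size. The one mention of retention, in the TEENS+ description, concerns an earlier study and carries no figure.

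**The concern.** The number recruited and the number powered are identical, although the same plan makes imputation the basis of its primary analyses and so expects some outcomes to be missing. The outcome is a change between two visits. A participant's change is observed only if both the 4-month and the 12-month BMI were obtained, so a missed visit at either time counts as loss.

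The power sentence is where a reader learns how large a PAC-PWL difference this trial can detect, and it bears on how a null result would be read. If some outcomes are missing, the difference detectable with 80% power may be larger than the sentence implies, and the reader cannot tell by how much. The estimate, its confidence interval and the test are not affected.

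**Working it through.** **Inputs from the documents.** Two-sided alpha .05, 105 per arm and d = .39 (power paragraph); 1:1 allocation of 210 families (Study Protocol). The power method is not named, so I used a two-sample t test.

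**Formula.** With n per arm, the noncentrality is d × √(n/2), with 2n − 2 degrees of freedom. Power is the probability that a noncentral t variable falls beyond the two-sided critical value.

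**Step 1: reproduce the stated figure.** For n = 105, the noncentrality is .39 × √52.5 = 2.826, with 208 degrees of freedom and critical value 1.971. Power is 80.3%. The normal approximation gives 80.7%. Both agree with the plan. Because d is printed to two decimals, I also tried its rounding range: d = .385 gives 79.3% and d = .3949 gives 81.3%.

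**Step 2: look for a reserve.** At d = .39, n = 104 gives 79.9%. So 105 is the smallest whole number per arm that reaches 80% by the t test, and it equals the number randomized. A 1% loss leaves 105 × .99 = 103.95 per arm and 79.9% power. (By the normal approximation 104 per arm still gives 80.3%, and 103 gives 79.9%, so the reserve is then one participant per arm.)

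**Step 3: illustrate loss.** The documents give no loss rate, so the rates below are assumptions. Loss means a missing 4-month or 12-month BMI. The approximation sets n = 105 × (1 − loss), keeps d = .39 for power, and solves for the d that gives 80% power. BMI units are that d × 2.9, the SD ceiling.

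| Assumed loss | n per arm | Power at d = .39 | d detectable at 80% | BMI units at SD 2.9 |
|---|---|---|---|---|
| 0% | 105 | 80.3% | .388 | 1.13 |
| 5% | 99.75 | 78.3% | .399 | 1.16 |
| 10% | 94.5 | 76.0% | .410 | 1.19 |
| 20% | 84 | 71.0% | .435 | 1.26 |
| 30% | 73.5 | 65.1% | .465 | 1.35 |

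**Step 4: why this is not a lower bound.** Suppose the 20% lost are imputed with no difference between arms. The average effect becomes .8 × .39 = .312. Even with n = 105 and no imputation variance, power is then 61%, below the 71% in the table. In the other direction, imputation that recovers information through auxiliary variables and the other visits would do better than the table.

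**Step 5: effect of the SD ceiling.** The raw difference is not stated; .39 × 2.9 = 1.131 is implied. Holding that fixed, an SD of 2.6 gives d = 1.131/2.6 = .435, hence 88.0% power with complete data and 80.0% at 20% loss. At 10% loss, 80% power holds at an SD of about 2.76.

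**The case against.** The strongest reply is that the stated figure is right, and that the primary analysis is a mixed model on multiply imputed data, so completers-only power describes an analysis the plan treats as additional. Imputation may recover part of the loss, and an SD below 2.9 with the same raw difference would offset more of it. Much of this stands. It is why the table is an approximation, and why the point is minor. But the power paragraph claims no gain from imputation and gives no within-person correlation from which one could be calculated. It links the increased SD to the 12-month projection, not to attrition.

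A reader might infer that the available-data figures are a floor and that imputation can only improve on them. The documents do not support that. Step 4 gives a counterexample, and the plan itself calls the complete-case analyses less conservative than the intention-to-treat ones.

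A reader might also infer that the trial is underpowered or should have enrolled more families. That does not follow either: no loss rate is given, the realised SD may be below the ceiling, and the size of any shortfall is unknown.

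It can also be said that rewording a planning sentence in a document dated October 2025 changes no visible decision. That argues for low severity, not for leaving the condition unstated.

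**Conclusion.** The point holds as a minor gap in disclosure. At the stated d and SD ceiling, the >80% claim is met only if essentially all 105 randomized per arm contribute a 4-12 month BMI change; by the t test, about 1% information loss takes it below 80%. That complete data was assumed is an inference from the recruited number equalling the smallest number that reaches 80%. It is strong, but it depends on the t test and on d = .39 as printed.

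The size of the effect depends on retention, which the documents do not give. At assumed losses of 10% and 20%, the available-data approximation gives about 76% and 71% power. The planned analysis may do better or worse, depending on the missingness and the imputation model. The moderator and mediator power statements rest on the same 210 and also state no allowance; I did not recompute them.

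**What to change.** State the expected proportion of randomized adolescents with both the 4-month and the 12-month BMI, or the observed proportion if it is known. Restate the power and the detectable difference at that retention, keeping the planning d and SD and not the observed effect. For example:

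*The >80% figure applies if all 105 randomized per arm contribute a 4-12 month BMI change. Counting a missing 4-month or 12-month BMI as loss, an available-data approximation with 20% loss gives about 71% power for d = .39, and the d detectable with 80% power is about .43 (1.26 BMI units at SD 2.9). The imputed mixed-model analysis may have higher or lower power, depending on the missingness and the imputation model. An SD below 2.9 with the same raw difference would raise power.*

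The 20% is a placeholder, and the figures that follow from it should be replaced together with it. Assumed rates of recovery by imputation should not be printed as results, because the documents give no basis for them.

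The cost is a few sentences and a less favourable stated power. No added enrolment and no change to the analysis is proposed.
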